1.2. Study Schema

The study schema is presented in Figure 1.

Figure 1: Study Schema

Abbreviations: D = Day; EOS = end of study; IST = internal safety team; mRNA = messenger RNA; N = number of participants.

- a. Participant must be 12 weeks old at Day 1.
- b. Arm 2 will begin enrollment after IST review of safety data collected from 25 participants in Arm 1 who have reached Day 64 (1 week after second dose of 5 μg).
- c. At selected dose level from Part 1.

Protocol: mRNA-1273-P206, Original

1.3. Schedule of Assessments

 Table 1:
 Schedule of Assessments (Part 1 and Part 2)

	0	1	2	3		4	5	6	7			8			9	USV
Visit Number	,	-			~====					~-			~-			
Type of Visit	С	С	С	TM	SFU	С	С	TM	С	SFU		С	SFU		С	С
Month Time Point		M0	M0		SC	M2	M2		M3	eDiary	SC	M8	eDiary	SC	M14	Up to M14
Study Visit Day	D-28 to D1 (Screening) ¹	D1 (Baseline)	$\mathrm{D4}^2$	D8	D29 ³	D57 ⁴	$D60^2$	$\mathrm{D64^4}$	D854.5	Every 4 weeks D99 – D211 ^{4,6}	Every 4 weeks D113–D225 ^{3,4}	D237	Every 8 weeks D265–D377 ⁴ .6	Every 8 weeks D293–D405 ^{3, 4}	D422 365 days after D57 ^{3, 4}	Unscheduled Visit ^{7, 8}
Window Allowance (Days)	_	_	±1	+ 3		-14/+ 7	±1	+ 3	-14/+ 7	± 7	± 7	± 14	± 7	± 7	± 14	N/A
Days Since Most Recent Injection	-	0	3	7	28	57	3	7	28	_	_	180	_	_	365	
ICF, demographics, concomitant medications, medical history ⁹	X															
Review of inclusion and exclusion criteria	X	X														
Physical examination and vital signs including length/height, weight and body temperature ¹⁰	X	X	X			X	X		X			X			X	X
Randomization		X														
Study injection ¹¹		X				X										
Blood sample for vaccine immunogenicity ¹²		X							X			X			X ⁷	
Blood sample for SARS-CoV-2 surveillance ¹³		X							X			_				
Nasal swab sample for SARS-CoV-2 ¹³	_	X				X			X			X			X	X

Protocol: mRNA-1273-P206, Original

Y72 1. X7	0	1	2	3		4	5	6	7			8			9	USV
Visit Number		1		-	O.D.I.				·	a.	3F 7		a.	3 T T	-	
Type of Visit	С	С	С	TM	SFU	С	С	TM	С	SFU		С	SFU		С	С
Month Time Point		M0	M0		SC	M2	M2		M3	eDiary	SC	M8	eDiary	SC	M14	Up to M14
Study Visit Day	D-28 to D1 (Screening) ¹	D1 (Baseline)	$\mathrm{D4}^2$	D8	D29 ³	D57 ⁴	$\mathrm{D}60^2$	$\mathrm{D}64^4$	D854.5	Every 4 weeks D99 – D211 ^{4, 6}	Every 4 weeks D113-D225 ^{3, 4}	D237	Every 8 weeks D265–D377 ^{4, 6}	Every 8 weeks D293–D405 ^{3, 4}	D422 365 days after D57 ^{3, 4}	Unscheduled Visit ^{7,8}
Window Allowance (Days)	_	_	±1	+ 3		-14/+ 7	±1	+ 3	-14/+ 7	± 7	± 7	± 14	± 7	± 7	± 14	N/A
Days Since Most Recent	_	0	3	7	28	57	3	7	28	_		180	_		365	
Injection	_	U	3	/	20	37	3	/	28	_	_	180	_	_	303	
Surveillance for COVID-19/illness visit ⁷				X	X	X		X	X	X	X	X	X	X	X	X
eDiary activation for recording solicited ARs (7 days) ⁸		X				X										
Review of eDiary data			X	X			X	X								
Follow-up safety telephone calls ¹⁴					X						X			X		
Recording of unsolicited AEs		X	X	X	X	X	X	X	X							
Recording of MAAEs, SAEs, and AESIs and concomitant medications and procedures relevant to or for the treatment of the MAAE and SAE ¹⁵		X	X	X	X	X	X	X	X	X	X	X	X	X	X	X
Recording of concomitant medications and procedures and nonstudy vaccinations ¹⁶		X	X	X	X	X	X	X	X		X	X		X	X	X

Abbreviations: AE = adverse event; AESI = adverse event of special interest; AR = adverse reaction; C = clinic visit; COVID-19 = coronavirus disease 2019; D = day; eCRF = electronic case report form; EDC = electronic data capture; eDiary = electronic diary; FDA = Food and Drug Administration; ICF = informed consent form; IRB = institutional review board; LAR = legally acceptable representative; M = month; MAAE = medically attended adverse event; N/A = not applicable; RT-PCR = reverse transcriptase polymerase chain reaction; SAE = serious adverse event; SARS-CoV-2 = severe acute respiratory syndrome coronavirus 2; SC = safety (telephone) call; SFU = safety follow-up; TM = telemedicine visit or call; USV= unscheduled visit.

Protocol: mRNA-1273-P206, Original

Note: In accordance with FDA Guidance on Conduct of Clinical Trials of Medical Products During COVID-19 Public Health Emergency (FDA March 2020), investigators may convert study site visits to home visits or telemedicine visits (with the exception of Screening, Day 1, Day 57, Day 85, Day 237, and Day 422) with the approval of the Sponsor (home visits also require site IRB approval).

- Screening Visit and Day 1 may be combined on the same day. Additionally, the Screening Visit may be performed over multiple visits if performed within the 28-day screening window.
- 2. Day 4 and Day 60 clinic visits will only be performed in Part 1 of study.
- 3. Safety follow-up via a safety telephone call will be performed on Day 29, every 4 weeks from Day 113 to Day 225, and every 8 weeks from Day 293 to Day 405.
- 4. If the visit for the second dose (Day 57) is disrupted and cannot be completed at Day 57 (-14/+7 days) as a result of the COVID-19 pandemic (self-quarantine or disruption of study site activities following business continuity plans and/or local government mandates for "stay at home" or "shelter in place"), the visit window may be extended to Day 57 + 14 days. When the extended visit window is used, the remaining study visits should be rescheduled to follow the intervisit interval from the actual date of the second dose.
- All scheduled study visits should be completed within the respective visit windows. If the participant is not able to attend a study site visit as a result of the COVID-19 pandemic (self-quarantine or disruption of study site activities following business continuity plans and/or local government mandates for "stay at home" or "shelter in place"), a remote evaluation via a telemedicine visit or call should be conducted in place of the study site visit (except for dosing visits and visits that require a blood draw). The remote evaluation should encompass all scheduled visit assessments that can be completed remotely, such as assessment for AEs and concomitant medications (eg, as defined in scheduled safety telephone calls). Home visits will be permitted for all nondosing visits, with the exception of screening, if a participant cannot visit the study site as a result of the COVID-19 pandemic. Home visits must be permitted by the study site IRB and the participant's parent(s)/LAR(s) via informed consent and have prior approval from the Sponsor (or its designee).
- 6. Safety follow-up via an eDiary questionnaire will be performed every 4 weeks from Day 99 to Day 211 and every 8 weeks from Day 265 to Day 377.
- An unscheduled visit may be prompted by reactogenicity issues, illness visit criteria for COVID-19, or new or ongoing AEs. If a participant meets the pre-specified criteria of suspicion for COVID-19, the participant will be asked to return within 72 hours or as soon as possible to the study site for an unscheduled illness visit to include a nasal swab sample (for RT-PCR testing to evaluate for the presence of SARS-CoV-2 infection) and other clinical evaluations. If a study site visit is not possible, a home visit may be arranged to collect the nasal swab sample and conduct clinical evaluations. The study site may collect an additional nasal swab sample for SARS-CoV-2 testing to be able to render appropriate medical care for the study participant as determined by local standards of care. Additionally, clinical information will be carefully collected to evaluate the severity of the clinical case.
- At each injection visit, participants' parent(s)/LAR(s) will record data into the eDiary starting approximately 30 minutes after injection under the supervision of the study site staff to ensure successful entry of assessment. Participants' parent(s)/LAR(s) will continue to record entries in the eDiary after they leave the study site, preferably in the evening and at the same time each day, on the day of injection and for 6 days following injection. Capturing details of ARs in the eDiary should not exceed 7 days after each vaccination. If a solicited local or systemic AR continues beyond Day 7 after vaccination, the event should be reviewed by the study site staff either via a telephone call or at an unscheduled study site visit.
- 9. Verbal medical history is acceptable.
- A full physical examination and vital signs assessments, including length/height, weight, and body temperature, will be performed at the Screening Visit (and on Day 1, if Day 1 and Screening Visit occur on separate days). Symptom-directed physical examinations and vital signs assessments will be performed on Day 1, Day 4 (in Part 1), Day 57, Day 60 (in Part 1), Day 85, Day 237, Day 422, and USV, and may be performed at other time points at the discretion of the investigator. Body temperature should be measured on each injection day prior to injection. Body temperature must be measured via the axillary route and any axillary reading of ≥ 37.8°C/≥ 100°F may be confirmed by a rectal measurement. On each injection day before injection and again 7 days after injection, the injection site should be examined. Any clinically significant finding identified during a study visit should be reported as an MAAE.

Protocol: mRNA-1273-P206, Original

Participants who are febrile ($\geq 38.0^{\circ}$ C/ $\geq 100.4^{\circ}$ F) before injection on Day 1 or Day 57 must have the visit rescheduled within the relevant visit window to receive the injection. Afebrile participants with minor illnesses may be injected at the discretion of the investigator.

- 11. Study injection postdose observation will be 60 minutes for Part 1 and 30 minutes for Part 2.
- On Day 1, sample must be collected prior to randomization and dosing. If a Day 1 (baseline) blood sample cannot be obtained, the participant could be rescheduled within the allowable screening period one time. If a blood sample still cannot be obtained at the rescheduled visit, then the participant will be considered a screen failure due to inability to satisfy inclusion criterion 3.
- The nasal swab and blood sample (collected before dosing on each injection day and on other scheduled days per the SoA) will be used to ascertain the presence or history of SARS-CoV-2 infection via RT-PCR and serum binding antibody specific to SARS-CoV-2 nucleocapsid, respectively.
- Medically qualified and trained study site personnel will call all participants to collect information relating to any MAAEs, SAEs, AEs leading to study withdrawal and information on concomitant medications associated with those events and any nonstudy vaccinations. In addition, study personnel will collect information on known participant exposure to someone with known COVID-19 or SARS-CoV-2 infection and on any COVID-19 symptoms the participant may experience.
- A list of AESIs pertinent to this study is maintained by the Sponsor and provided to each investigator. All SAEs and AESIs will be reported to the Sponsor or designee immediately and in all circumstances within 24 hours of becoming aware of the event via the EDC system. If a site receives a report of a new SAE or AESI from a study participant or receives updated data on a previously reported SAE or AESI and the eCRF has been taken offline, then the site can report this information on a paper SAE or AESI form using the SAE Mailbox, the SAE Hotline, or the SAE Fax line.
- All concomitant medications and procedures will be recorded through 28 days after each injection (through the completion of the Day 85 visit). All nonstudy vaccines given at any time during the study period should be recorded. All concomitant medications relevant to or for the treatment of an SAE, MAAE, or AESI will be recorded from Day 1 through the final visit (Day 422).

Page 33

Protocol: mRNA-1273-P206, Original

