8.10. Safety Assessments

Safety assessments will include monitoring and recording of the following for each participant, according to the SoA (Table 1):

- Solicited local and systemic ARs (Section 8.11.3) that occur during the 7 days following each injection (ie, the day of injection and 6 subsequent days). Solicited ARs will be recorded daily using eDiaries (Section 8.10.2).
- Unsolicited AEs observed or reported during the 28 days following each injection (ie, the day of injection and 27 subsequent days). Unsolicited AEs are defined in Section 8.11.1.
- AEs leading to discontinuation from Day 1 through EoS.
- MAAEs (Section 8.11.4) from Day 1 through EoS.
- SAEs (Section 8.11.2) from Day 1 through EoS.
- AESIs (Section 8.11.5) from Day 1 through EoS.
- Assessments for SARS-CoV-2 infection from Day 1 through EoS (Section 8.9.3.1).

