- Body temperature measurement should be performed at approximately the same time each day using the thermometer provided by the study site. If body temperature is taken more than once in a given day, only the highest temperature reading should be recorded. Body temperature must be measured via the axillary route and any axillary reading of ≥ 37.8°C/≥ 100°F may be confirmed by a rectal measurement.
- Measurement, as applicable, for solicited local ARs (injection site erythema and swelling/induration); the size measurements will be performed using the ruler provided by the study site.
- Any medications taken to treat or prevent pain or fever on a day of injection or for the next 6 days.

The eDiary will be the only source document allowed for solicited systemic or local ARs (including body temperature measurements). Participants' parent(s)/LAR(s) will be instructed to complete eDiary entries daily. Quantitative temperature recordings and measurement of any injection site erythema or swelling/induration reported on the following day may be excluded from the analyses of solicited ARs.

Study site staff will review eDiary data with participants' parent(s)/LAR(s) at telemedicine visits 7 days after each injection in both Part 1 and Part 2. eDiary data will also be reviewed during the additional visits 3 days after each injection (ie, on Day 4 and Day 60) in Part 1 only.

The eDiary will be used every 4 weeks, starting at Day 99 through Day 211 and every 8 weeks, starting at Day 265 through Day 377, to capture the occurrence of AEs, MAAEs, SAEs, AESIs, or AEs leading to withdrawal. As specified in the SoA (Table 1), the eDiary will prompt the participant's parent(s)/LAR(s) to complete an eDiary questionnaire that collects the following data:

- Changes in health since last completing the questionnaire or since in contact with the study site
- Any MAAEs, AESIs, or SAEs
- Known close contact with someone in the household who has known COVID-19 or SARS-CoV-2 infection. An infected person can spread SARS-CoV-2 starting 2 days before they have any symptoms (or, for asymptomatic people, 2 days before the positive specimen collection date) through 10 days after symptom onset (or, for asymptomatic

Protocol: mRNA-1273-P206, Original

people, 10 days after positive test). Per the CDC, "close contact" to someone with COVID-19 is defined as follows:

- o Being within 6 feet for a total of 15 minutes or more
- o Providing care at home

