8.11.11. Time Period and Frequency for Collecting AE, AESI, MAAE, and SAE Information

Medical occurrences that begin before the start of IP dosing but after obtaining informed consent/assent will be recorded in the Medical History/Current Medical Conditions section of the eCRF and not in the AE section; however, if the condition worsens at any time during the study, it will be recorded and reported as an AE.

Adverse events may be collected as follows:

- Observing the participant
- Receiving an unsolicited complaint from the participant's parent(s)/LAR(s)
- Questioning the participant's parent(s)/LAR(s) in an unbiased and nonleading manner

Solicited ARs will be collected from the day of injection through 6 days after each dose. Other (unsolicited) AEs will be collected from the day of injection through 28 days after each dose.

Serious AEs, AESIs, and MAAEs will be collected from the start of IP dosing until the last day of study participation at the time points specified in the SoA (Table 1).

All SAEs and AESIs will be recorded and reported to the Sponsor or designee immediately and in all circumstances within 24 hours of becoming aware of the event via the EDC system. If a site receives a report of a new SAE or AESI from a study participant or receives updated data on a previously reported SAE or AESI and the eCRF has been taken offline, then the site can report this information on a paper SAE or AESI form using the SAE Mailbox, the SAE Hotline, or the SAE Fax line (Section 8.11.10).

An abnormal value or result from a clinical or laboratory evaluation can also indicate an AE if it is determined by the investigator to be clinically significant (eg, leads to dose modification or study drug discontinuation, or meets any serious criteria, or is considered an AESI). If this is the

Protocol: mRNA-1273-P206, Original

case, it must be recorded in the source document and as an AE on the appropriate AE form(s). The evaluation that produced the value or result should be repeated until that value or result returns to normal or is stabilized and the participant's safety is not at risk.

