- b) study day on or after the date of the first injection but before the second injection (if applicable) will be calculated as: date of assessment/event date of the first injection + 1;
- c) study day on or after the date of the second injection will be calculated as: date of assessment/event date of the second injection + 1; if study day is on the same day as the second injection, date and time will be compared with the second injection date and time. If time is prior to the time of second injection, then study day is calculated as: date of assessment/event date of the first injection + 1; If it is after the time of second injection or the time is missing or not available then study day is calculated as: date of assessment/event date of the second injection + 1.

For calculation regarding antibody levels/concentrations, antibody values reported as below LLOQ will be replaced by 0.5 × LLOQ. Values that are greater than the upper limit of quantification (ULOQ) will be converted to the ULOQ if actual values are not available, and actual values will be used if available. Missing results will not be imputed.

The following analysis periods or stages for safety analyses will be used in this study:

- Up to 28 days after any vaccination: this stage starts at the day of each vaccination and continue through the earliest date of (the day of each vaccination and 27 subsequent days, next vaccination [if applicable]). This analysis period will be used as the primary analysis period for safety analyses including unsolicited AE, except for solicited AR, unless specified otherwise.
- Overall period (throughout the study): this analysis period starts at the first injection on Day 1 and continues through the earliest date of (study completion, discontinuation from the study, or death).

Unscheduled visits: Unscheduled visit measurements will be included in analysis as follows:

- In scheduled visit windows per specified visit windowing rules.
- In the derivation of baseline/last on-treatment measurements.
- In the derivation of maximum/minimum on-treatment values and maximum/minimum change from baseline values for safety analyses.
- In individual subject data listings as appropriate.

Visit windowing rules: The analysis visit windows for protocol-defined visits are provided in Appendix B.

Incomplete/missing data:

- Imputation rules for missing prior/concomitant medications, non-study vaccinations and procedures are provided in Appendix C.

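### Scheduled recording of unsolicited AEs ends at a Day 85 visit that may be held 14 days early, leaving up to 13 of the 28 days after Dose 2 without it

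*Protocol*

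**What the plan says.** Protocol Section 8.10 sets the collection period as "Unsolicited AEs observed or reported during the 28 days following each injection (ie, the day of injection and 27 subsequent days"), and Section 8.11.6 gives the same count. Section 8.11.11 runs one day longer: "unsolicited) AEs will be collected from the day of injection through 28 days after each dose". None of the three ends collection at a visit.

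The SAP (Section 6.1) takes "the day of each vaccination and 27 subsequent days", cut short by the next vaccination if there is one, and adds: "This analysis period will be used as the primary analysis period for safety analyses including unsolicited AE". SAP Section 6.3.1 uses the number of subjects in the Safety Set as denominator.

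The schedule works by visit. In protocol Table 1 the row "Recording of unsolicited AEs" is marked at Days 1, 4, 8, 29, 57, 60, 64 and 85, and at no later contact or unscheduled visit. The Day 85 window is -14/+7 days. SAP Appendix E repeats the row and the window. The row for MAAEs, SAEs and AESIs continues through Day 422 and includes unscheduled visits.

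The next contacts are the Day 99 eDiary and the Day 113 call. Sections 8.10.1 and 8.10.2 say that both cover AEs generally. The Table 1 footnote on calls is narrower: staff "call all participants to collect information relating to any MAAEs, SAEs, AEs leading to study withdrawal". The eDiary item list in Section 8.10.2 names "Any MAAEs, AESIs, or SAEs", together with a general item on changes in the infant's health since the last questionnaire or site contact.

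**The concern.** Section 8.11.9 ties the investigator's AE reporting to the times in the schedule, so blank cells in Table 1 can govern what sites do. A visit two weeks early is within the protocol, yet it comes before the safety window has closed. A site working from Table 1 and the call footnote could then stop asking about ordinary unsolicited AEs while the primary period is still running. The SAP would still count that infant as fully observed.

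The Dose 1 window does not have this weakness. It runs from Day 1 to Day 28, and the row is marked at Day 29 (SAP Appendix E allows that call only to be late, +3 days) and again at Day 57.

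At stake is under-ascertainment of a primary safety endpoint. It weighs most in Part 1, which is open-label without placebo and informs dose selection from absolute rates. SAP Section 7 reports 18 participants in Part 1 Arm 2 at the enrollment pause, so one infant whose only event is missed moves that arm's rate by 1/18 = 5.6 percentage points.

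**Working it through.** **Inputs.** Dose 2 on Day 57 (window -14/+7), Day 85 visit (window -14/+7), and 28 days since the most recent injection at Day 85, all from Table 1. Safety window of the injection day plus 27 days, from Section 8.10 and SAP Section 6.1.

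**The plan's own figure.** 85 - 57 = 28 days since Dose 2, as Table 1 states. A visit on the nominal day therefore covers the whole window, which runs from Day 57 to Day 84.

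**Formula.** Days with scheduled recording = visit day - Dose 2 day + 1, capped at 28, counting the visit day as recorded. Days without = 28 minus that number.

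**Day 85 window anchored to the actual Dose 2 date**

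| Visit offset | Days recorded | Days without |
|---|---|---|
| -14 | 14 + 1 = 15 | 13 (46%) |
| -7 | 21 + 1 = 22 | 6 |
| -2 | 26 + 1 = 27 | 1 |
| -1 or later | 28 | 0 |

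These results hold for any Dose 2 date. They include the extended window, where Dose 2 on Day 71 puts the earliest re-anchored visit on Day 85 and again leaves 13 days.

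**Day 85 window anchored to Day 1 (earliest visit Day 71)**

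| Dose 2 on Day | Days without |
|---|---|
| 43 | 0 |
| 50 | 6 |
| 57 | 13 |
| 60 | 16 |
| 64 | 28 - (71 - 64 + 1) = 20 (71%) |

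The documents do not state this anchor.

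**Sensitivity to counting.** If the visit day is not counted as recorded, 13 becomes 14 and 20 becomes 21. Under the longer period in Section 8.11.11 (29 calendar days), the 13 also becomes 29 - 15 = 14.

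**Distance to the next contact.** The Day 99 eDiary (±7 days, Day 92 to Day 106) falls 21 to 35 days after a Day 71 visit. The Day 113 call is nominally 42 days after it.

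**Illustration only.** Assume Dose 2 on Day 57 and visits spread uniformly over Days 71 to 92 (22 possible days). Visits on Days 71 to 83 leave 13, 12, ..., 1 days uncovered. The share affected is 13/22 = 59%, and the mean over all infants is 91/22 = 4.1 days. The documents give no visit distribution, so both figures rest on that assumption.

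**The case against.** The strongest reply is that collection is defined by days since injection, whatever the visit date, and that later contacts can pick up what an early visit misses. Section 8.10.2 says the eDiary captures AEs, and its health-change item reaches back to the last site contact. Section 8.10.1 includes AEs in the call interview. Section 8.11.6 has a standard question on health changes at every visit or telephone contact, and Section 8.11.9 sends every unsolicited AE reported or observed to the AE page. MAAEs, SAEs and AESIs are recorded to Day 422 in any case. All of this stands. It rules out several stronger readings that a reader might infer:

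- **That the days after an early visit go unrecorded.** The passages above contradict this. What is missing is scheduled recording, and only for events that are not MAAEs, SAEs or AESIs.
- **That 20 days are exposed.** This requires a Day 1 anchor and Dose 2 on Day 64. Table 1 gives 28 days since the most recent injection at Day 85, and Section 4.1.1.2 describes Day 85 as 28 days after Dose 2, so both point to Dose 2 as the anchor. Explicit re-anchoring is written only for the extended window, which leaves the matter unstated.
- **That the lost days convert into a lost incidence.** Scaling the unsolicited AE rate quoted in Section 2.3.2 for older children would assume no later capture. It would also count medically attended and serious events as lost, and borrow from a different product and age group.
- **That rates after Dose 2 cannot be set beside those after Dose 1.** The SAP summarises unsolicited AEs up to 28 days after any vaccination and over the whole study. It specifies no such comparison by dose.

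In Part 2 both arms follow the same schedule under observer blinding, so the documents give no reason to expect early visits to differ by arm.

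The reply does not remove the contradiction. The call footnote and the eDiary's named AE categories are narrower than the text of Sections 8.10.1 and 8.10.2. A general health question three to five weeks after the visit is a weak net for minor events.

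**Conclusion.** The point holds as an internal contradiction with a bounded consequence. Table 1 and SAP Appendix E can end scheduled recording of unsolicited AEs before the period required by Sections 8.10, 8.11.6 and 8.11.11, and used by the SAP as primary, has run out. The firm figure is 13 of 28 days for an infant seen at -14 days, counting the visit day as recorded. Infants seen no more than one day early lose nothing on the 28-day count. The 20-day figure is conditional on an anchor that the documents do not state.

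Any bias is downward. Its size cannot be computed from the documents, because it depends on how many visits are early, how many AEs fall outside the MAAE, SAE and AESI categories, and how well the later contacts recover them. The consequence is modest, but it touches a primary safety endpoint and can arise without any protocol deviation. Correction is worthwhile.

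**What to change.** Reconcile the passages as follows:

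1. In Table 1 and SAP Appendix E, carry the unsolicited-AE row to the first existing contact on or after 27 days post Dose 2. Where the Day 85 visit was held earlier than that, this is normally the Day 99 eDiary contact.
2. Have that contact ask explicitly for any AE with onset within 27 days after Dose 2.
3. Align the call footnote and the Section 8.10.2 item list with that question, and bring the day count in Section 8.11.11 into line with Section 8.10.
4. State whether the Day 85 window is anchored to the actual Dose 2 date.
5. Report, by group, how many infants had the full 28-day window after Dose 2 observed. This remains useful if collection is already complete.

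The cost is one schedule row, one script line, small text edits and one summary count, with no added visit. The drawback is slightly longer parental recall at a contact that already takes place.
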